4.2.2 The Chinese version of Pediatric Quality of Life Inventory 4.0 (PedsQL 4.0)

The PedsQL is a well-established instrument for assessing health-related quality of life in children and adolescents aged 2-18 years (Varni et al., 2005). This study will use the Chinese version of PedsQL 4.0 Generic Core Scales, which include 23 items across four domains: physical functioning (8 items), emotional functioning (5 items), social functioning (5 items), and school functioning (5 items). Responses are scored on a 5-point Likert scale (0 = never a problem, 4 = almost always a problem), then transformed to a 0-100 scale, where higher scores reflect better health-related quality of life. The PedsQL yields a total scale score (average of all 23 items), a physical health summary score (average of the 8 physical functioning items), and a psychosocial health summary score (average of the 15 items across emotional, social, and school functioning domains). These scores provide a comprehensive assessment of overall quality of life and specific physical and psychosocial

health outcomes, enabling exploration of how sleep disturbances correlate with broader well-being in children with cancer, other chronic illnesses, and healthy controls. Parent-proxy reports for younger children and self-reports for older participants, mirroring the PSQI administration. The PedsQL 4.0 Generic Core Scale has undergone cross-cultural adaptation into Chinese and psychometric validation, rendering it suitable for application in clinical settings (Ji et al., 2011; Yeung et al., 2012). The Chinese version of PedsQL will serve as a secondary measure to explore how sleep disturbances correlate with broader quality-of-life outcomes, such as fatigue-related physical limitations or emotional distress, which are particularly pertinent to children with chronic illnesses like cancer.

4.3 Key Variables

4.3.1 Primary Outcome Variable

Sleep quality, measured by the global PSQI score, will be the primary endpoint. This encompasses the seven component scores (e.g., sleep duration, latency, efficiency), providing a holistic assessment of sleep health. A global score >5 will classify participants as having poor sleep quality, enabling prevalence comparisons across groups.

4.3.2 Secondary Outcome Variable

Health-related quality of life, assessed via the PedsQL total score and its domain-specific subscales (physical, emotional, social, school), as well as physical health summary score and psychosocial health summary score will examine the broader impact of sleep disturbances. This will help determine, for example, whether poor sleep in children with cancer correlates with reduced emotional or physical functioning compared to other groups.

4.3.3 Demographic Variables

To control for potential confounding effects on sleep patterns and access to healthcare resources, the following demographic and clinical variables will be collected: age (in years), gender, socioeconomic status (SES), disease type, disease status, and use of hypnotics (yes/no). SES will be assessed through parental education (categorized as primary or below, junior secondary, senior secondary, or university/college and above). For children with cancer, disease type (e.g., leukemia, lymphoma, brain tumor, bone tumor, or others) and disease status (e.g., stage 1-4, recurrence, years since diagnosis, treatment type such as chemotherapy, radiotherapy, surgery, immunotherapy, transplant, or combination) will be recorded. For children with other chronic illnesses, disease type (e.g., asthma, type 1 diabetes, chronic kidney disease) will be noted. These factors may influence sleep outcomes, e.g., older children may report greater daytime dysfunction, or lower parental education level may limit access to supportive care, necessitating adjustment in statistical analyses to isolate the effects of chronic illness on sleep quality.

4.4 Expected Outcomes

This study anticipates uncovering significant differences in sleep quality between children hospitalized with cancer, those with other chronic illnesses, and healthy children. The following outcomes are expected:

4.4.1 Children with Cancer

It is hypothesized that children with cancer will exhibit the most severe sleep disturbances among the three groups. Factors such as pain associated with the illness, side effects of chemotherapy, and frequent nighttime medical interventions are likely to result in reduced sleep duration, prolonged sleep latency, and increased sleep fragmentation. Reported data from the PSQI are also expected to place a majority of children with cancer above the clinical threshold for poor sleep.

4.4.2 Children with Other Chronic Illnesses

While children with other chronic illnesses are also expected to experience sleep disturbances, these disruptions are likely to be less severe than those observed in children with cancer. For example, conditions such as asthma or diabetes may cause episodic sleep interruptions (e.g., nocturnal coughing or nighttime glucose monitoring), but they are not typically compounded by the environmental and psychological stressors associated with hospitalization. A smaller percentage of this group is anticipated to exceed the clinical threshold for poor sleep on the PSQI.

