1.2 Comparison with Healthy Children and Other Chronic Illnesses

In contrast, healthy children generally experience more consistent and undisturbed sleep accentuates how chronic illnesses combined with hospitalization damage children's sleep quality. Children with other chronic illnesses also encounter sleep difficulties yet their reasons for these issues differ from those diagnosed with cancer. For instance, the condition of asthma triggers nighttime awakenings because of wheezing and coughing, while diabetic patients experience disrupted sleep due to fluctuating glucose levels (Adavadkar et al., 2022; Meltzer & Mindell, 2017). These conditions cause sleep interference but patients tend to experience less psychological and physical distress from cancer which leads to milder overall sleep issues.

2. Study Objectives

The objectives of this study are threefold:

- 1) To assess the prevalence and nature of sleep disturbances in children with cancer.
- 2) To compare sleep disturbances in children with cancer to those in healthy children and children with other chronic diseases.
- 3) To identify potential factors contributing to sleep disturbances in paediatric patients.

3. Study Significance

This study contributes to the comprehension of pediatric sleep disturbances by carefully evaluating sleep disruptions among three groups: children with cancer, children with other chronic illnesses, and healthy children. The data generated from this study provides vital information for developing targeted therapies specific to population groups with linked sleep disturbance factors. By pinpointing specific contributors, such as hospital environment, medication effects, or pain, the research will lay the groundwork for targeted interventions. These could include reducing nighttime disruptions, refining pain management, or designing sleep-friendly hospital settings. Furthermore, integrating tools like the Chinese version of PSQI into routine care could enable early detection and management of sleep issues, mitigating long-term risks like cognitive and emotional deficits

Beyond oncology, the study's comparison with children who have other chronic illnesses will reveal how different conditions uniquely disrupt sleep, guiding tailored strategies for diverse patient groups. The healthy control group will establish a benchmark for normal sleep, highlighting the extent of disruption caused by chronic illness and elevating sleep as a priority in pediatric care.

4. Methods

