5.1 Children with Cancer (n=50)

Participants in this group will be children with a confirmed cancer diagnosis, such as leukemia, lymphoma, or solid tumors, who are currently hospitalized for treatment at the inpatient oncology wards of Hong Kong Children's Hospital. Eligible participants must be actively receiving cancer-directed therapy (e.g., chemotherapy, radiation) during their hospital stay. Inclusion criteria require that participants, or their parents or legal guardians as proxies, can provide accurate reports about sleep patterns, either through self-assessment or observation, ensuring reliable data collection. This group will capture the acute impact of cancer treatment and hospitalization on sleep, a critical focus of the study.

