5.2 Children with Other Chronic Illnesses (n=50)

This group will comprise children diagnosed with chronic conditions other than cancer, such as asthma, type 1 diabetes, or chronic kidney disease, recruited from the cardiac, nephrology, and mixed wards of Hong Kong Children's Hospital. These illnesses are selected for their known potential to disrupt sleep—e.g., nocturnal asthma symptoms or glucose instability—while differing in pathophysiology from cancer. Participants must be under active management for their condition and currently hospitalized, but must not have a history of primary sleep disorders (e.g., narcolepsy, obstructive sleep apnea) unrelated to their chronic illness. This criterion ensures that observed sleep disturbances are attributable to the chronic condition rather than pre-existing sleep pathology.

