5.4 Exclusion Criteria

Across all three groups, children will be excluded if they are not Chinese and are in intensive care units. Children who exhibit severe cognitive impairments that preclude accurate reporting of sleep experiences, either by themselves or their parents or legal guardians, will be excluded. Additionally, participants with neurological conditions known to independently affect sleep, such as epilepsy or cerebral palsy, will be excluded to avoid confounding the primary relationship between chronic illness and sleep disturbances. The use of sedative medications unrelated to the participant's primary condition (e.g., for behavioral management rather than cancer treatment) will also disqualify participants, as these could artificially alter sleep patterns and obscure study outcomes. These exclusion criteria ensure that sleep disturbances observed are primarily linked to the participants' health status rather than extraneous factors.

6. Procedure

Participants will be enrolled following informed parental consent and, for children under 18, age-appropriate assent, as detailed in the ethical approval section. Recruitment will occur at Hong Kong Children's Hospital for the cancer and chronic illness groups, while healthy controls will be recruited from siblings of sick children or children of hospital staff. Once enrolled, parents or legal guardians and participants will receive the demographics, the Chinese version of PSQI and PedsQL surveys in paper format, depending on preference, with instructions provided by trained research staff. Completing the questionnaires is estimated to take approximately 15-20 minutes. For hospitalized children (the cancer and chronic illness groups), surveys will be completed during their inpatient stay to capture real-time sleep experiences, and the study team will collect completed questionnaires on the same day. Healthy children can return their questionnaires via their parents/legal guardians, one extra visit may be required by the parents/legal guardians.

7. Statistical Analysis

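### Section 4.4.2 assumes hospitalisation stressors are atypical for a chronic-illness group that 5.2 and 6 make inpatients, and ill-versus-healthy differences are joint effects of illness and hospitalisation that sections 3, 4.3.3 and partly 5.2 credit to illness alone

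*Protocol*

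**What the plan says.** **The expectation.** Section 4.4.2 predicts less severe disturbance in the chronic-illness group than in the cancer group. It illustrates this with asthma and diabetes, whose sleep interruptions are described as episodic, and adds that "they are not typically compounded by the environmental and psychological stressors associated with hospitalization".

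**The sample.** Section 5.2 sets the entry requirement for that group: "Participants must be under active management for their condition and currently hospitalized". The children are "recruited from the cardiac, nephrology, and mixed wards" of the study hospital. Children with cancer are "currently hospitalized for treatment at the inpatient oncology wards" (section 5.1). Section 6 confirms the setting of data collection: "For hospitalized children (the cancer and chronic illness groups), surveys will be completed during their inpatient stay to capture real-time sleep experiences". Healthy controls are siblings of patients or children of staff, and their questionnaires come back through their parents (sections 5.3 and 6).

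**What the comparison is said to show.** Section 3 describes the healthy group as a benchmark, "highlighting the extent of disruption caused by chronic illness". Section 4.3.3 says the listed variables call for adjustment so that what chronic illness does to sleep can be singled out. Section 5.2 says that excluding primary sleep disorders lets disturbances be ascribed to the chronic condition and not to earlier sleep pathology. By contrast, 1.2 and 4.4.3 name illness and hospitalisation together, and 5.1 names cancer treatment and hospitalisation together.

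**The promise on contributors.** Section 3 goes on: "By pinpointing specific contributors, such as hospital environment, medication effects, or pain", the research is to prepare the ground for interventions, among them "reducing nighttime disruptions, refining pain management, or designing sleep-friendly hospital settings".

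**The concern.** There are two linked problems.

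First, a reason offered for what this study's chronic-illness group will show describes such children outside hospital, whereas the study enrols them only in hospital.

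Second, the only children not in hospital are the healthy ones. A difference between an ill group and the healthy group could come from the disease and its treatment, from sleeping on a ward, or from both. If the report follows the wording of section 3 or 4.3.3, it will credit to illness a difference that the design cannot divide.

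This matters for use of the results. Section 3 lists an illness-side intervention (pain management) next to ward-side ones (fewer night-time disruptions, better hospital settings). The three group means alone cannot say which side a difference comes from.

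**Working it through.** **No planned figure to reproduce.** The relevant numbers are 150 children, 50 per group (section 5). The protocol gives no effect size, standard deviation or target power for them, and this point does not depend on them. The check is one of consistency and identifiability.

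**Step 1: the expectation against the sample.** Section 4.4.2 reasons from hospitalisation being atypical for these conditions. Section 5.2 requires hospitalisation of every child in the group, and section 6 collects the data during the stay. In this sample, being or not being in hospital cannot produce a difference between the two ill groups, because both are wholly inpatient. The reasons in 4.4.1 (pain, chemotherapy side effects, night-time medical interventions) do not rely on it.

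**Step 2: can illness and hospitalisation be separated?** Code each child with an intercept and indicators for cancer, chronic illness and inpatient:

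| Group (n) | Intercept | Cancer | Chronic | Inpatient |
|---|---|---|---|---|
| Healthy (50) | 1 | 0 | 0 | 0 |
| Chronic illness (50) | 1 | 0 | 1 | 1 |
| Cancer (50) | 1 | 1 | 0 | 1 |

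In every row, inpatient = cancer + chronic. The 150-row matrix has 4 columns and rank 3. Adding one column each for age, gender and socioeconomic status gives 7 columns and rank 6. With parental education as three indicators for its four categories, it is 9 columns and rank 8. One column is always redundant. Further covariates do not help, because the identity between the columns remains.

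**Step 3: what each contrast estimates.** Let a_c and a_k be the effects of cancer and of chronic illness, and h_onc and h_non the effects of being an inpatient on an oncology or a non-oncology ward. Then:

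- cancer − healthy = a_c + h_onc
- chronic − healthy = a_k + h_non
- cancer − chronic = (a_c − a_k) + (h_onc − h_non)

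With arbitrary values, chosen only to show the ambiguity:

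| a_c | a_k | h_onc | h_non | Cancer − healthy | Chronic − healthy | Cancer − chronic |
|---|---|---|---|---|---|---|
| 2 | 1 | 0 | 0 | 2 | 1 | 1 |
| 0 | 0 | 2 | 1 | 2 | 1 | 1 |
| 1 | 0 | 1 | 1 | 2 | 1 | 1 |
| 1 | 1 | 1 | 0 | 2 | 1 | 1 |

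An all-illness account, an all-hospital account and two mixtures give the same three differences. If h_onc = h_non, the hospital term drops out of cancer − chronic. If ward type or length of stay differs between the groups, part of it can remain.

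**Step 4: is hospital exposure named anywhere?** Section 4.3.3 lists age, gender, socioeconomic status, disease type, disease status and use of hypnotics. The predictor examples in section 7 are type of cancer treatment and pain levels. Neither names ward, length of stay or another measure of hospital exposure. Among the 100 inpatients, a model with intercept, cancer and nights in the current stay has 3 columns and rank 3, provided nights vary within groups. An association with nights could therefore be estimated if nights were recorded.

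**The case against.** Much can be said for the protocol. The sentence in 4.4.2 is an illustration about conditions in general, it is softened by an adverb, and no test, endpoint or sample size rests on it. The phrase in section 3 belongs to a statement of significance and is not a definition of the estimand. The adjustment sentence in 4.3.3 is prompted by age and parental education and does not mention hospitalisation. The one in 5.2 contrasts the chronic condition with earlier sleep disorders only. Sections 1.2, 4.4.3 and 5.1 already use joint wording.

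This limits the reach of the point but does not remove it. The 4.4.2 sentence is still given as a reason for what a wholly inpatient group will show. Sections 3 and 4.3.3 still promise an attribution that the design rules out, and the protocol disagrees with itself on what the contrast means.

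Three stronger readings are tempting, and the documents do not support them:

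- *The expected ordering of the groups has lost its basis.* It has not; the reasons in 4.4.1 stand.
- *The protocol presents cancer versus chronic illness as a pure cancer effect.* No passage says so. Ward and length of stay are cautions for interpretation, and section 5.2 does not define its mixed wards, so the overlap of wards between groups is unknown.
- *Hospital exposure will certainly go unrecorded.* The section 7 predictors are only examples, and section 10 counts clinical records among the data. What can be said is that no listed variable measures it.

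**Conclusion.** The point holds as one of rationale and interpretation. One stated reason in 4.4.2 does not apply to the sample defined in 5.2 and 6. Both comparisons with healthy children estimate illness plus current hospitalisation, and this is exact: 4 columns, rank 3, whatever covariates are added. It rests only on the protocol's own eligibility rules and on healthy controls not being inpatients.

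Sections 3 and 4.3.3, and in part 5.2, claim more than this design can deliver. How far a report using that wording would mislead cannot be quantified, since the protocol gives no size for a hospitalisation effect.

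A reader might infer that the group comparison itself is invalid. It is not: the ANOVA still compares the three groups as enrolled, and the number of children and the significance level are unaffected. The wording should be corrected, and a decision on recording hospital exposure is needed before data collection, because the survey is completed once.

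**What to change.** 1. Reconcile 4.4.2 with 5.2 and section 6, so that the reasons for the expected ordering fit a chronic-illness group made up of inpatients.
2. Reword sections 3, 4.3.3 and 5.2 in line with 1.2, 4.4.3 and 5.1: cancer-versus-healthy and chronic-versus-healthy differences are to be reported as the joint effect of illness and current hospitalisation.
3. Name cancer versus chronic illness as the comparison not aliased with being an inpatient, and note that ward type and length of stay may still differ between those groups.
4. For the hospital-environment promise in section 3, choose one of two courses. Either take nights in the current stay and ward from the chart and examine nights as an exploratory contributor among the two inpatient groups, or remove hospital environment from the contributors to be pinpointed. If nights are used, call them a proxy: section 1.1 describes the hospital environment as night-time procedures, noise and lighting, and nights measure none of these.

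The cost is text edits, two chart items if the first course is taken, and narrower stated conclusions.

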4.4.3 Healthy Children

Healthy children are expected to demonstrate the highest sleep quality among the three groups, with results showing near-optimal sleep duration and efficiency. Reported data are anticipated to reflect low levels of sleep disturbances, with the majority of children scoring below the clinical threshold on the PSQI. These findings will provide a baseline for understanding how chronic illnesses and hospitalization affect sleep outcomes.

5. Study Population

This study will enroll Chinese children aged 6 to 18 years, divided into three distinct groups based on their health status: children with cancer, children with other chronic illnesses, and healthy children. A total sample size of 150 participants (50 per group) will be targeted to ensure adequate statistical power for comparative analyses. Recruitment will occur at Hong Kong Children's Hospital or the cancer and chronic illness groups, and healthy children will be recruited from healthy siblings of participants or the healthy children of hospital staff with specific inclusion and exclusion criteria applied to each group to maintain homogeneity and minimize confounding variables.

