5.3 Healthy Children (n=50)

The healthy control group will be of adequate sample size. These include siblings of pediatric patients (both oncology and non-oncology wards), and children of hospital staff (e.g., nurses, administrative personnel). Inclusion criteria require no history of chronic illness, psychiatric disorders, or known sleep conditions. Parental consent and child assent will be obtained for all participants.

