Data will be analyzed using SPSS (version 29), a powerful statistical software package designed for clinical research. Descriptive statistics such as means, standard deviations, and frequencies, will summarize demographic characteristics (e.g., age, gender distribution), as well as PSQI global and component scores, and PedsQL total and subscale scores for each group. To compare sleep quality and health-related quality of life across the three groups, a one-way analysis of variance (ANOVA) will be used for continuous variables (e.g., PSQI global score, sleep duration, PedsQL physical functioning score). For secondary analyses, multiple linear regression will examine the relationships between sleep quality (PSQI score) and potential predictors (e.g., type of cancer treatment, pain levels) while adjusting for confounding factors such as age, gender, and socioeconomic status (SES). Pearson or Spearman correlations will be utilized to assess the relationships between PSQI and PedsQL scores, helping to evaluate the impact of sleep disturbances on health-related quality of life. A p-value of less than 0.05 will indicate statistical significance, and effect sizes (e.g., eta-squared) will be reported to quantify the magnitude of differences.

8. Parental Consent and Children's Assent

Ensuring the ethical participation of children in this study requires a dual approach, involving obtaining informed consent from parents or legal guardians and, where appropriate, obtaining assent from the children themselves.

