Protecting the privacy and confidentiality of participants is a paramount concern in this study. To protect patient privacy, all research data would be handled in line with Hospital Authority/Hospital's policy in handling/storage/destruction of patients/ medical records. All data collected including demographic information, clinical records, the Chinese version of the PSQI, and the Chinese version of PedsOL 4.0,

will be de-identified using unique participant codes rather than names or other identifiable markers. These codes will be stored separately from the data in a password-protected electronic file accessible only to authorized research personnel. Physical records, such as consent forms, will be kept in a locked cabinet within a secure ward manager's office at Hong Kong Children's Hospital. Electronic data will be stored on an encrypted, institution-approved server compliant for safeguarding protected health information. Access to the data will be restricted to the principal investigator and trained research staff directly involved in the study, and no identifiable information will be disclosed in publications or presentations. Upon study completion, data will be retained for a minimum of five years, after which it will be securely destroyed. Paper records shredded, and electronic files permanently deleted to prevent unauthorized access. In the event of an incidental finding (e.g., severe untreated sleep apnea), the research team will notify the participant's parents/legal guardian and healthcare provider while maintaining confidentiality, ensuring appropriate follow-up care without breaching privacy protocols.

11. Ethical Considerations

The issue of confidentiality will be solved by recording the data in a manner that does not allow the participants to be identified (i.e. using a non-recognizable code for each patient). The study will be conducted in compliance with Declaration of Helsinki.

References

Adavadkar, P. A., Pappalardo, A. A., Glassgow, A. E., Zhang, C., Schwartz, A., Brooks, L. J., & Martin, M. A. (2022). Rates of diagnoses of sleep disorders in children with chronic medical conditions. *Journal of Clinical Sleep Medicine, 18*(8), 2001–2007. <https://doi.org/10.5664/jcsm.10064>

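### Healthy controls may share a family with enrolled patients or with each other, but the fixed analyses treat all children as independent and no family code or control source is listed for collection

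*Protocol*

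**What the plan says.** Three places in the protocol describe where healthy children come from.

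- Section 5: "healthy children will be recruited from healthy siblings of participants or the healthy children of hospital staff".
- Section 5.3: "These include siblings of pediatric patients (both oncology and non-oncology wards), and children of hospital staff".
- Section 6: "healthy controls will be recruited from siblings of sick children or children of hospital staff".

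Section 5 speaks of siblings of participants, so a control may be related to an enrolled patient. Sections 5.3 and 6 are wider and also admit siblings of patients who are not in the study. None of the three fixes a sibling/staff split, a matching rule or a limit per family.

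For the comparison of groups, Section 7 states that "a one-way analysis of variance (ANOVA) will be used for continuous variables". It adds multiple linear regression adjusted for factors such as age, gender and SES, and Pearson or Spearman correlations between PSQI and PedsQL. No family term appears.

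The collection list in Section 4.3.3 is short ("age (in years), gender, socioeconomic status (SES), disease type, disease status, and use of hypnotics (yes/no") and contains neither a family link nor the type of control. Under Section 10 the data "will be de-identified using unique participant codes rather than names or other identifiable markers". The code file and consent forms are kept apart from the data.

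Section 3 gives the control group its purpose: "The healthy control group will establish a benchmark for normal sleep".

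**The concern.** Siblings resemble each other, and here the measurement adds to it. Section 4.2.1 has parents complete the PSQI for younger children, so one parent may rate two children of the same family. SES is parental education, which siblings living with the same parents share. If such children are analysed as unrelated, the standard errors of cancer versus healthy and chronic illness versus healthy are wrong.

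The direction depends on the kind of link. A patient-sibling pair lies across the two groups compared, so its correlation reduces the variance of the difference. Ignoring it makes the test conservative and discards precision. Two siblings inside the healthy group carry less information than two unrelated children, so ignoring that link makes the test anti-conservative.

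A second matter follows from the same gap. Siblings of hospitalised children and children of hospital staff are different populations. If the source is not recorded, there is no routine way to check that both give the same benchmark for normal sleep.

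**Working it through.** **Inputs from the protocol.** 50 children per group (Section 5); global PSQI as primary endpoint (Section 4.3.1); significance at p < 0.05 (Section 7), taken as two-sided. Section 5 says that "A total sample size of 150 participants (50 per group) will be targeted to ensure adequate statistical power for comparative analyses", but gives no effect size, SD or target power, so that claim cannot be reproduced. For orientation, under independence 50 per group gives 80% power for a pairwise difference of 0.56 SD.

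**Assumptions.** The protocol gives no within-family correlation and no pair counts. I take the correlation ρ as 0.2 to 0.5 and vary m, the number of patient-sibling pairs within one contrast, and k, the number of sibling pairs within the healthy group.

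**Formula.** With common variance σ² and independent children, the healthy-minus-patient difference has variance 2σ²/50.

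- Each cross-group pair subtracts 2ρσ²/50².
- Each healthy-healthy pair adds 2ρσ²/50².
- Dividing by 2σ²/50 gives the ratio of true to assumed variance: R = 1 − ρ(m − k)/50.

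The planned SE is wrong by a factor 1/√R. The true type I error is 2[1 − Φ(1.96/√R)].

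| Links in the contrast | R (ρ = 0.2; 0.5) | Planned SE | True type I error |
|---|---|---|---|
| m = 12 | 0.952; 0.880 | 2.5%; 6.6% too large | 0.045; 0.037 |
| m = 25 | 0.900; 0.750 | 5.4%; 15.5% too large | 0.039; 0.024 |
| k = 5 | 1.02; 1.05 | 1.0%; 2.4% too small | 0.052; 0.056 |
| k = 25 | 1.10; 1.25 | 4.7%; 10.6% too small | 0.062; 0.080 |

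The row m = 12 corresponds to about 25 sibling controls divided between the two patient groups. The row m = 25 puts them all in one contrast. The row k = 25 needs every control to arrive with a sibling and none to be related to a patient.

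**Power.** At an assumed difference of 0.5 SD the independent-groups SE is √(2/50) = 0.2 SD. Power is Φ((0.5/0.2 − 1.96)/√R) with the planned SE and Φ(0.5/(0.2√R) − 1.96) with the correct one.

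- m = 12: 0.710 against 0.726 (ρ = 0.2); 0.718 against 0.760 (ρ = 0.5).
- m = 25: 0.715 against 0.750 (ρ = 0.2); 0.734 against 0.823 (ρ = 0.5).

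**Check by simulation of the three-group ANOVA** (40,000 runs per cell, ρ = 0.5).

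- 12 cancer-sibling and 12 chronic-sibling pairs: overall F test 0.039, cancer versus healthy 0.037, chronic versus healthy 0.038, cancer versus chronic 0.050.
- 25 healthy-healthy pairs: F test 0.076, cancer versus healthy 0.078, cancer versus chronic 0.052.

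**Both kinds of link together** (20,000 runs). With ten cancer families and ten chronic-illness families each giving two sibling controls, and five staff families giving two each, the F test rejects at 0.053 to 0.057. For one contrast m = 20 and k = 25, so R = 1 + 5ρ/50 = 1.02 to 1.05, which agrees.

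**Pooled PSQI-PedsQL correlation.** With the same family correlation in both scores, the Pearson test rejects at about 0.052 to 0.074 across the linked scenarios simulated, against 0.051 with no links.

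**The case against.** The strongest reply is that the effect is small and, for patient-sibling links, on the safe side. With 12 pairs per contrast the false-positive rate falls and the power lost is 1.6 to 4.2 percentage points. The figure of 0.080 needs an arrangement that the protocol nowhere suggests, and mixed links largely cancel. All of this stands and limits the weight of the point.

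The assumed correlation may also be generous for patient-sibling pairs. The patient reports sleep during an inpatient stay while the sibling is at home, and the reporter may differ by age within a pair. Sections 5.3 and 6 admit siblings of children who are not enrolled, who create no link to a patient. These are fair reasons to favour the lower end of the ranges. A regression confined to the cancer group, such as one on type of cancer treatment, involves no controls and is largely unaffected.

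Finally, clustered standard errors are commonly left to an SAP, which may exist. Section 4.3.3 may not be the whole form: pain levels, a predictor named in Section 7, are missing from it too. Staff will know at enrolment how each control was found, and some links could be rebuilt from the code file and consent forms. But an SAP cannot reliably model a link that was never planned for collection. A sibling of a non-enrolled patient could not be told from a staff child through any enrolled relative. The gap is in data capture, so it is best closed before enrolment.

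**Conclusion.** The point holds. The protocol allows related children into the healthy group, fixes analyses that assume unrelated ones, and does not plan to record what would be needed to correct this. The affected results are the two contrasts with healthy children, the overall ANOVA, and regressions or correlations pooled over groups.

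The distortion is modest under plausible pair counts and can go either way. It should not be read as a general inflation of type I error, and it does not invalidate the study. Every size given rests on the assumed family correlation and pair counts. That two controls may be siblings is inferred from the absence of a per-family limit. The loss of a check on the benchmark by control source does not depend on those assumptions. This is a change that should be made because it is cheap and hard to make later.

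**What to change.** 1. Add two fields to the paper form: a family code shared by all enrolled children of one family, and the control's source (oncology sibling, non-oncology sibling, staff child). List both in Section 4.3.3.
2. In Section 7, fit the group comparison with a family random intercept or with standard errors clustered by family, and treat regressions and correlations pooled over groups likewise. With few pairs the family correlation will be poorly estimated: for about 24 pairs and ρ = 0.2 its standard error is near (1 − 0.2²)/√24 = 0.20. Clustered standard errors avoid having to estimate it.
3. Report the healthy group's PSQI by source as a sensitivity check on the benchmark.
4. Use the same description of eligible siblings in Sections 5, 5.3 and 6. A limit of one healthy child per family is optional once clustering is modelled.

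The cost is two form fields and a slightly longer analysis. Sample size and recruitment stay as they are.
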